### **13.6.3 Correlative Endpoints**

#### **13.6.3.1 Global DNA Methylation**

DNA methylation, using LINE-1 assay, will be determined and expressed as continuous variables with mean, median, and standard deviation calculations reported. Average changes in global DNA methylation will be assessed at baseline and every two weeks for the first eight weeks of the study. Disease control rates (DCR) and time to event endpoints (PFS and OS) will

be estimated for patients who have methylation below the median compared to above the median at baseline. We will also estimate these outcomes for those who achieve low methylation (<10% methylation) compared to normal methylation ( $\geq 10\%$  methylation) after eight weeks of therapy. We will also estimate these outcomes for those who achieve a change in methylation greater than the median compared to lower than the median at eight weeks compared to baseline.

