#### **15.2.7 Exploratory and Ancillary Studies**

See [Section 13.6.3](#) for description of correlative studies. All subjects will be required to agree to an on treatment biopsy after 8 weeks of therapy. Given the patient population and the likelihood that some subjects will have disease or clinical progression precluding biopsies we estimate that we will obtain on-treatment biopsy samples from a minimum of 20 subjects.

- 15.2.7.1 Global DNA Methylation will be assessed in all subjects at baseline and every 2 weeks for the first 8 weeks of study. We will estimate the disease control rates (DCR) and time to event endpoints (median PFS and median OS) for subjects who have methylation below the median compared to above the median at baseline. We will also estimate these outcomes for those who achieve low methylation (<10% methylation) compared to normal methylation ( $\geq 10\%$  methylation) after 8 weeks of therapy. We will also estimate these outcomes for those who achieve a change in methylation greater than the median compared to higher than the median at 8 weeks (compared to baseline).
- 15.2.7.2 Fisher's exact test will be performed to compare the disease control rate for the two groups. Kaplan-Meier estimates of the survival distribution for the two groups will be calculated, and the two groups will be compared using a log-rank test. Change in methylation in tumor tissue will be evaluated in 20 patients who undergo baseline and week eight biopsies and will be compared using the paired t-test or the Wilcoxon signed-rank test depending on the data distribution. With 20 patients, we will have 80% power to detect a change of 0.66 standard deviations given an alpha of 0.05.
- 15.2.7.3 Change in methylation in tumor tissue will be evaluated in subjects who undergo baseline and week 8 biopsies. We will describe changes in specific gene methylation patterns as described in [Section 13.6.3](#).
- 15.2.7.4 Immune phenotyping will be measured on the subjects who undergo an on-treatment tumor biopsy. We will provide descriptive tables of IHC expression of CD8/CD3 T cell ratio, CD86/CD68 macrophage ratio, PD1 expression. Samples will be compared between pre and post combination specimens in treated subjects using the paired t-test.

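### Global methylation is measured as a continuous variable but related to DCR, PFS and OS only through two-group splits, which may cost roughly a third of the information in the baseline comparison

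*Combined protocol and SAP*

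**What the plan says.** Section 13.6.3.1 sets the scale of measurement: "DNA methylation, using LINE-1 assay, will be determined and expressed as continuous variables". It then relates methylation to DCR, PFS and OS through three comparisons, each of two groups:

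- **Baseline level**, at the sample median. Outcomes will "be estimated for patients who have methylation below the median compared to above the median at baseline".
- **Week-8 level**, at a fixed cut: under 10% methylation against 10% or more.
- **Week-8 change from baseline**, at the sample median: "change in methylation greater than the median compared to lower than the median at eight weeks compared to baseline".

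Section 15.2.7.1 repeats all three, but words the last as "those who achieve a change in methylation greater than the median compared to higher than the median at 8 weeks". Section 15.2.7.2 supplies the tests: "Fisher's exact test will be performed to compare the disease control rate for the two groups", and for the survival distributions "the two groups will be compared using a log-rank test". Neither section plans a Cox, logistic or other model with methylation as a continuous term for these relationships.

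The tissue analysis in 15.2.7.2 is different. Change in tumor methylation is tested by a paired t-test or signed-rank test without grouping, and it carries the only power statement given for methylation (20 patients, 0.66 SD, 80%).

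**The concern.** Cutting a continuous marker in two treats a subject just above the cut the same as one far above it. With 31 subjects there is little information to spare, and a real association between methylation and outcome becomes easier to miss. Section 1.1 hopes for a blood marker that helps predict who may benefit. A cut at this sample's own median does not carry over to another cohort, whereas an effect per unit or per SD with an interval does.

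The two week-8 comparisons raise a further problem. PFS and OS are timed from first treatment (13.6.1.1, 13.6.1.2), but the groups are known only at week 8, so a subject must stay on study that long to be classified. A continuous model on the same clock would have the same problem.

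**Working it through.** **1. The plan's own methylation figure.** Paired t-test, n = 20, difference 0.66 SD, alpha 0.05, from the noncentral t distribution with 19 df and noncentrality 0.66 × √20 = 2.95. Two-sided power is 79.9% and one-sided 88.5%. The stated 80% is reproduced as a two-sided test. No power is stated for the split-by-outcome comparisons, so steps 2 to 6 rest on assumptions given here.

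**2. Information kept by a split.** For a linear effect this is the squared correlation between the marker X and its group indicator. For a normal X cut so that a share p lies below the cut c, it is φ(c)² / [p(1−p)].

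- At the median, φ(0)² / 0.25 = 0.1592 / 0.25 = 2/π = 0.637, a loss of 36.3%.
- Effective size: 31 × 0.637 = 19.7. To match 31 subjects analysed continuously, a split needs 31 × π/2 = 48.7.
- The documents give no LINE-1 distribution. The loss at the median for other shapes is 25% (uniform), 48% (lognormal, log-SD 0.5) and 52% (exponential).
- The share below the fixed 10% cut is not given. Under normality the median is the least costly single cut, so the loss there is at least 36.3%. If 20% fell below it, for example, the figure kept would be 0.280² / 0.16 = 0.49.

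**3. PFS power, baseline split.** Inputs: 31 subjects, 18 months' accrual and 6 months' follow-up (15.2.5), so censoring is uniform from 6 to 24 months. PFS is taken as exponential with the target median of 4 months at the mean marker value, and the marker as normal with a log-linear effect. With λ = ln 2 / 4 = 0.173, the event probability at the mean is 1 − (e^(−6λ) − e^(−24λ)) / (18λ) = 0.892, or 31 × 0.892 = 27.6 events. Two-sided 0.05, 6,000 simulated trials per row:

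| HR per SD | Continuous (Cox score) | Median split (log-rank) |
|---|---|---|
| 1.0 | 5.5% | 6.0% |
| 1.4 | 37% | 26% |
| 1.6 | 61% | 43% |
| 1.8 | 78% | 58% |
| 2.0 | 88% | 70% |

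A rerun with 20,000 trials gave 77% and 58% at 1.8. False-positive rates are similar, so the gap is not bought by a liberal continuous test.

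**4. DCR power, baseline split.** Assumed DCR 50% at the mean marker value, 31 subjects. Logistic score test against Fisher's exact test: odds ratio per SD 1.8, 31% and 11%; 2.5, 61% and 28%; 3.0, 74% and 40%. Part of this gap is Fisher's own conservatism (simulated size about 1.4%), not the split.

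**5. Week-8 comparisons.** These cannot use 31 subjects. Eight weeks is 56 / 30.44 = 1.84 months. With exponential PFS, 31 × 0.5^(1.84/2) = 16.4 subjects are progression-free then at a 2-month median, and 31 × 0.5^(1.84/4) = 22.5 at a 4-month median. Section 15.2.7 itself expects at least 20 on-treatment biopsies. At n = 20, even the continuous test has about 57% power at a hazard ratio of 1.8, and the effective size after a median split is 20 × 0.637 = 12.7. If blood is the source, 12.1.6.6 schedules draws at baseline and weeks 3, 5 and 6, with none at week 8.

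**6. When the split wins.** If the hazard truly steps at the median (HR 2.5 between halves, n = 31), the split has about 50% to 53% power and the continuous test about 43% to 44%, depending on how the baseline hazard is set.

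**7. Wording of the change split.** Section 13.6.3.1 sets greater against lower than the median; 15.2.7.1 sets greater against higher, which describes one group twice.

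**The case against.** The strongest reply is that these are exploratory comparisons with no power claim and no decision rule, and that median-split curves are easy to read. That stands, and it limits the weight of the point. It is also true that the size of the loss depends on a distribution and effect shape the documents do not give, and that a threshold effect would favour the split. The plan, however, offers no biological reason for a threshold at the sample median.

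Some stronger readings are tempting but not supported:

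- A reader might infer that every comparison is cut at the sample median. The week-8 level uses a fixed 10% cut, so the objection that a cut will not transfer to another cohort does not apply to it. It is still a dichotomy.
- A reader might take this as the main test of the trial's mechanism. Sections 13.6.3.2 and 13.6.3.3 place that in paired tissue profiling and immune phenotyping, and 15.2.7.2 analyses tissue change without grouping.
- A reader might apply the 31-subject power figures to all three comparisons. They fit only the baseline split.
- A reader might conclude from 15.2.7.1 that the change analysis is undefined. It is a one-word slip: 15.2.7 refers back to 13.6.3, where the contrast is correct.

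The one subject at the median, left in neither group when the number analysed is odd, is a trivial matter.

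**Conclusion.** The point holds as a minor one. A marker declared continuous is related to DCR, PFS and OS only through two-group splits. For the baseline split the expected loss is about 36% under a normal marker with a linear effect, and 25% to 52% across the shapes tried. At a hazard ratio of 1.8 per SD that is a drop in power of about 20 percentage points with 31 subjects. The conclusion rests on an effect that rises smoothly with methylation; it reverses for a step at the median. The week-8 comparisons have too few subjects for strong conclusions by either method and also need a later time origin. Nothing here affects the primary PFS analysis.

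**What to change.** In 13.6.3.1 and 15.2.7.1–15.2.7.2:

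- Make the main exploratory analysis a Cox model for PFS and for OS and a logistic model for DCR, each with methylation as a continuous term (per SD or per unit) and a 95% interval. Use a penalised or exact logistic fit if the data are sparse.
- Keep the median and 10% groups for Kaplan-Meier curves and descriptive tables.
- For week-8 level or change, start PFS and OS follow-up at a week-8 landmark among subjects still at risk, and state how many that is.
- State whether the week-8 value comes from blood or tissue, and reconcile this with the sampling times in 12.1.6.6.
- Correct 15.2.7.1 to greater against lower than the median, to match 13.6.3.1.

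The modelling and wording changes need no new subjects. The cost is a linearity assumption, to be checked with a residual plot, and fewer subjects in the landmark analyses.

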#### **13.6.3.2 Epigenetic effect in tumor tissue**

The premise of our proposal is that hypomethylation of tumor cells and/or stromal cells results in a significant polarization of the immune response seen in pancreatic cancer and this leads to an increase in response to tumor checkpoint inhibition. Our preliminary data provides strong support for this, however this study provides a unique opportunity to understand the dynamic changes that occur in the tumor. Therefore we will first assess the impact of the systemically administered demethylating agent on tumor tissue. This assessment is performed in all 31 patients 8 weeks after completion of TCI therapy. Core biopsies are obtained and tumor tissue is microdissected for methylation profiling using the Illumina 800K platform. Comparison is made to the pre-treatment tumor biopsy. The Herbert Irving Comprehensive Cancer Center Epigenetics Core Laboratory (led by co-investigator [name], PhD) routinely performs this procedure and the subsequent statistical analysis and mapping of the resulting data to ENCODE tracks. Validation of up to 48 amplicons in up to 48 samples is done using the Fluidigm Access Array – Illumina MiSEQ platform. Here, bisulfite treatment and sequencing is performed to validate “hits” from the methylation array.

A subsequent validation step at the transcriptional and translational level will be performed

based on the classes of genes identified but include one of three strategies (1) RNASeq; (2) Q-PCR; (3) immunohistochemistry or immunofluorescence on concurrent biopsy specimens. In cases where sufficient quantity of tumor material is obtained to perform RNASeq analysis this will be pursued. The parallel use of methylation and expression profiling allows for the selection of functionally most relevant genes. Although there is support for the feasibility of sufficient amount of high quality RNA obtained from endoscopic biopsies to perform RNASeq as we are uncertain whether in each case this will be feasible the alternative strategies may also be pursued.

#### 13.6.3.3 Immune phenotyping

It is our hypothesis that azacitidine will have significant impact on immune polarization in the tumor and potentially the number of PD1 or PDL1 positive cells. We have recently shown and validated the ability to score expression of epithelial markers and inflammatory cell markers in pancreatic cancer endoscopic core biopsies. We therefore will evaluate the expression of the ratio of CD8/CD3 T cells, CD86/CD68 macrophages and PD1 and PD1L expression using immunohistochemistry.

The ratio of CD8/CD3 TILs and CD86/CD68 macrophages will be calculated and expressed as a continuous variable with mean, median, and standard deviation calculations reported. We will compare pre- and post-treatment CD8/CD3 and CD86/CD68 ratios using a paired t-test or a nonparametric test based on the data distribution.

PD-L1 expression at baseline will be quantified as a dichotomous variable (>1% expression considered positive, <1% considered negative). PD-L1 expression is reported to be higher in 81% of pancreatic tumors in historical controls than in paired non-malignant samples. Correlation between baseline PD-L1 expression (positive vs. negative) and response to therapy (patients with clinical benefit, as defined by radiographic response and disease control, and those without clinical benefit) will be analyzed using frequency tables and Fisher's exact test.

### 13.7. Unblinding Procedures

N/A- this is not a blinded study.

### 13.8. Stopping Rules

Early trial termination will be the result of the criteria specified below:

- Unacceptable aggregate toxicity as determined by the trial's Sponsor in consultation with the trial's DSMC
- Quality or quantity of data recording is inaccurate or incomplete
- Poor adherence to protocol and regulatory requirements
- Incidence or severity of adverse drug reaction in this or other studies indicates a potential health hazard to subjects
- Plans to modify or discontinue the development of the study drug

In the event of Merck decision to no longer supply study drug, ample notification will be provided so that appropriate adjustments to subject treatment can be made.

## **14. DATA REPORTING / REGULATORY REQUIREMENTS**

### **14.1. Data Collection**

Adverse event lists, guidelines, and instructions for AE reporting can be found in [Section 10.0](#) (Adverse Events: List and Reporting Requirements). The Data Safety Monitoring Plan is described in [Section 14.3](#).

The Herbert Irving Comprehensive Cancer Center has an electronic clinical trials and data management system (CTMS) that will be used for data collection. CRFs for the study will be built into the CTMS for data entry. The system has full auditing capabilities which is web-based and housed on a server in a fully HIPAA compliant server room with restricted access and video camera monitoring. All users must login with their own application username and password. Users off campus must first access the Virtual Private Network with their assigned campus username and password and then use their application credentials. Users are only able to see study information if they are indicated as study personnel in our electronic IRB system. Users are limited to access based on the role assigned in their corresponding protocol. Subject data is entered directly into the system, which (in the case of Columbia subjects) confirms the correct identity of patients via an interface with the electronic medical patient index. Staff with the appropriate IRB defined roles can run reports within the system for reporting purposes.

### **14.2. Data Reporting**

Case Report Forms will be completed for each subject enrolled into the clinical study through the CTMS. It is the investigator's responsibility for ensuring that all clinical and laboratory data entered on the corresponding CRFs are complete, accurate and authentic.

### **14.3. Data and Safety Monitoring Committee**

The NCI-approved Data Safety and Monitoring Committee (DSMC) of the Herbert Irving Comprehensive Cancer Center (HICCC) will monitor every subject who receives treatment on this protocol for toxicity. This protocol will adhere to the policies of the currently approved HICCC Data and Safety Monitoring Plan (DSMP), which is in accordance with NCI and CUMC-IRB policy and guidelines. The committee is chair is appointed by the HICCC Director. The committee consists of HICCC faculty and staff with expertise in oncology, research pharmacy, research nursing, and data management. The DSMC convenes twice a month to review patient safety and the conduct of the trial. The PI will submit data and safety monitoring reports to the DSMC at a frequency to be determined by the DSMC based on risk to the subjects.

At the time of renewal, the study team will submit the most recent DSMC approval letter for safety review to the CUMC IRB. Any modifications that are required by the DSMC to ensure patient safety will be submitted to the IRB. All protocol deviations, violations, and eligibility

waivers will be submitted to and approved by the DSMC prior to being reported to the IRB. All study data reviewed and discussed during these meetings will be kept confidential.

For multicenter research, the principal investigator will assure that there is a mechanism in place to distribute the report to all participating investigators for submission to their local IRB. The report will document that a review of data and outcomes across all centers took place on a given date. It will summarize the DSMC's review of the cumulative toxicities reported from all participating sites without specific disclosure by treatment arm. It will also inform site investigators of the study the DSMC's conclusion with respect to progress or need for modification of the protocol.

#### **14.4. Quality Control and Quality Assurance**

Independent monitoring of the clinical study for protocol and GCP compliance will be conducted periodically by the CPDM Compliance Core on behalf of the HICCC DSMC. Additionally, the Compliance Oversight Committee of the IRB at Columbia University Medical Center may audit the study at any time per institutional policies and procedures. The investigator-sponsor and Columbia University Medical Center will permit direct access of the study monitors and appropriate regulatory authorities to the study data and to the corresponding source data and documents to verify the accuracy of this data.

A risk-based approach will be used by the Compliance Core to determine the frequency, number of subject charts, and data elements to be monitored. The Compliance Coordinator will review the study status and summarize enrollment, toxicities, SAEs/UPs, dose escalation, statistical endpoints (e.g., stopping rules), etc. for the full DSMC membership at the regularly scheduled meetings.

##### **Internal On-site Monitoring:**

- Initial, recurrent, and close-out on-site monitoring visits will also be conducted at remote clinical sites, as appropriate/feasible. Other sites will have monitoring performed remotely (see below for further details).
- The study Monitoring Visit Log will be completed and signed by the monitor and the PI/CRNP/CRN and/or CRC and will be filed in the regulatory binder.
- The Compliance Coordinator will communicate with the site coordinator/Site Principle Investigator to schedule the monitoring visit and arrange for access to study materials and documentation.
- The assigned Compliance Coordinator will monitor IIT trials within 1 month after the first subject is enrolled and throughout the life of the study to ensure that the study is being conducted in accordance with the protocol, GCP, applicable federal and local regulations, and per all applicable SOPs. The Compliance Coordinator is responsible to notify the PI and CRNP/CRN/CRC of upcoming monitor visits and convey what information and documentation will be required for the visit(s). The Compliance Coordinator is responsible for verifying that informed consent is properly obtained, eligibility is met (via the central registration process), and all study procedures are conducted according to the study protocol. The Compliance Coordinator will also verify

that the data reported in the CRF's accurately reflect source documents, that all toxicities have been reported to date, and that all SAE's/UPs/deviations/violations have been reported according to local IRB and HICCC DSMC requirements. The Compliance Coordinator will issue queries and ensure resolution in a timely and efficient manner. The Compliance Coordinator will also monitor for applicable regulatory compliance and research pharmacy compliance (if applicable) and communicate any deficiencies as appropriate.

#### **14.5. Confidentiality**

Information about study subjects will be kept confidential and managed according to the requirements of the Health Insurance Portability and Accountability Act (HIPAA). Those regulations require a signed subject authorization informing the subject of the following:

- What protected health information (PHI) will be collected from subjects in this study
- Who will have access to that information and why
- Who will use or disclose that information
- The rights of a research subject to revoke their authorization for use of their PHI.

In the event that a subject revokes authorization to collect or use PHI, the investigator, by regulation, retains the ability to use all information collected prior to the revocation of subject authorization. For subjects that have revoked authorization to collect or use PHI, attempts should be made to obtain permission to collect at least vital status (e.g., that the subject is alive) at the end of their scheduled study period.

The subject binders will be maintained with in the CPDM offices, a secured floor within the Herbert Irving Pavilion and only the investigator and study staff will have access to the file.

#### **14.6. Source Documents**

Source data is all information, original records of clinical findings, observations, or other activities in a clinical trial necessary for the reconstruction and evaluation of the trial. Source data are contained in source documents Examples of these original documents, and data records include: hospital records, clinical and office charts, laboratory notes, memoranda, subjects' diaries or evaluation checklists, pharmacy dispensing records, recorded data from automated instruments, copies or transcriptions certified after verification as being accurate and complete, microfiches, photographic negatives, microfilm or magnetic media, x-rays, subject files, and records kept at the pharmacy, at the laboratories, and at medico-technical departments involved in the clinical trial.

